Willing and eligible participants will be randomly assigned to one of two treatment groups: 5 ml of cod liver oil x1 per day or placebo together with the first meal each day.

Concealment of allocation: Randomization will be conducted on the Department of Research Support, Oslo University Hospital, by personnel not involved in the study. The list of participants with address and treatment assignment will be provided to the packaging company, which will send cod liver oil or placebo for the whole study period to each participant based on that list. The responsible personnel at the packaging company will not be involved in the study, and no personnel involved in the study will have access to this list.

The number of participants to be randomized: In the case of successful recruitment of an excess number of participants, participants belonging to high-risk groups (> 70 years old and dark-skinned) will be prioritized for randomization. The remaining non-randomized participants will be included as an extra control group that will not receive any treatment but will otherwise be followed as the other participants and analyzed for the exploratory endpoints.

In the case fewer recruited participants than planned, Caucasians using cod liver oil or an equivalent supplement (vitamin D and omega 3) less frequently than 5 days per week can be included in the study We consider the risk of overdosing of omega 3 or vitamin D to be very low in this group and while the group will contribute less to the total power of the study than participants not using such supplements their intake will increase during the study period and they will contribute to the study. Based on data from Koronastudien we expect less than 20-30% such participants.

Unblinding

In the highly unlikely case of emergency unblinding this will be done the physician requiring unblinding contacting the PI and will be referred to the Research Support randomization team for information about treatment allocation.

Study Intervention Compliance

Our primary measure of compliance will be self-reported information provided on a monthly followup questionnaire, which will ask about adherence to the cod liver oil/placebo taking regimen. It has been reported that although most participants try diligently to adhere to the regimen, those who do not comply have no embarrassment about describing what they are actually doing. Blood levels have shown near-perfect correlations with self-reported questionnaire data on adherence[17]. Participants reporting taking cod liver oil or placebo more than two months will be considered compliant.

Because CLOC participants will reside throughout Norway, it will not be possible to obtain blood samples for a validity study on all participants. Thus, at baseline and approximately 3-4-months after starting taking cod liver oil/placebo we will invite randomly selected participants to provide a blood sample for biobanking and validation purposes, including measurement of 25(OH)D and EPA+DHA levels. The distribution of these values will be compared between the active and placebo groups, and compared with the questionnaire data on compliance, as a test for validity.

Additionally, we will be able to assess 25 (OH)D and EPA + DHA levels in the up to 10.000 randomly selected participants who will be asked to provide a blood sample at baseline and at the end of the

study. These blood samples may be collected as dried blood spots and will also be used for other analyses.

Dose modification

No dose modification will be conducted, but participants can divide doses freely.

Continued Access to Study Medication after End of the Study

Tran is available in all Norwegian grocery stores and participants will be encouraged to follow Norwegian dietary advice.

Treatment of Overdose

N/A

Concomitant Therapy

Any drugs will be allowed together with the oils. However, use of supplements containing vitamin D and other contents of cod liver oil are expected to reduce the power of the study to show a difference between the treatment groups and will be recorded. Participants will be encouraged not to begin with new dietary supplements while in the study, but they can continue in the study if the choose to do this. Participants will be referred to official Norwegian dietary advice online if they have questions about supplements or diet during the study period.

7. Discontinuation of Study Intervention and Participant

Discontinuation/Withdrawal

Discontinuation of Study Intervention

In rare instances, it may be necessary for a participant to permanently discontinue study intervention. If study intervention is permanently discontinued, the participant will remain in the study to be evaluated for relevant endpoints unless the participants want to also withdraw.

Participant Discontinuation/Withdrawal from the Study

A participant may withdraw from the study at any time at his/her own request or may be withdrawn at any time at the discretion of the investigator for safety, behavioral, or compliance reasons.

The participant will be permanently discontinued both from the study intervention and from the study at that time.

The participant may also withdraw the consent to use some of his or her data as described in the consent form.

Lost to Follow Up

A participant will be considered lost to follow-up if he or she repeatedly fails to return for scheduled visits and is unable to be contacted by the study and data on registries are no longer recorded (this will mostly be participants moving abroad).

Cod Liver Oil for Covid-19 Prevention Study, protocol version 1.2, November 10, 2021

8. Study Assessments and Procedures

Endpoint Ascertainment and Validation

Se also definition of endpoints in chapter 3.

Endpoint ascertainment will be done by obtaining endpoint data from relevant registries. The connection between the CLOC study and the registries will be made by the Norwegian Personal Identity Number (PIN), which ensures unambiguous identification of every subject. The PIN number is validated by 2-factor authentication when the informed consent is signed electronically.

Registry data will be compared to the self-reported symptoms. In cases where an episode of respiratory illness evidenced by a positive PCR or culture is not accompanied by a symptom report form, the patient will be encouraged to complete a symptom form.

Diagnoses in hospitalized patients and outpatient visits are reported to the Norwegian Patient Registry (NPR), while deaths are reported to the Causes of Death Registry.

Covid-19- related diagnoses and deaths in these registries are essential endpoints in the study and will be validated through inspection of the relevant hospital records (NPR) or hospital- or GP records (CDR). This will be done by contacting the hospital or GP for a copy of the relevant information from their records, which will be recorded in the CRF together with a conclusion about Covid-19 being the cause of the hospitalization or death. The information will also be presented for another independent and blinded physician for a second opinion, and in cases of discrepancy; the information will further be inspected by a blinded endpoint-verification committee for a final decision. It will be arranged for the endpoint-verification committee to have access to interview the treating physician.

The endpoint of subjective dyspnea during Covid-19 will be based on self-reporting (yes/no), but Covid-19 diagnosis is verified by the Norwegian Surveillance System for Communicable Diseases (MSIS).

Safety Assessment

Cod liver oil is recommended as a part of the Norwegian diet in official dietary recommendations and no safety assessment will be conducted during the cod liver oil/placebo taking period. See Ethics section.

Blood collection

Blood will be collected for the purpose of monitoring compliance and for the study itself. Blood will be collected according to the standard procedure described in Oslo University Hospitals' quality control system, and either venipuncture or dried blood spots will be used.

- Random blood collection for Compliance (either venipuncture or dried blood spot)
- Baseline and follow up for biobanking (either venipuncture or dried blood spot)
- Surplus material already stored in existing biobanks including treatment-biobanks will also be collected from the participants, and either stored in the study biobank or analyzed immediately (or both)

Blood samples will be analyzed for vitamin D levels (25(OH)D), EPA and DHA levels, and other biochemical parameters. The material will be stored in the study biobank for analyses to explore and explain the main results of the study. These analyses can include both biochemical, immunological, and molecular biology analyses and will be determined based on the results of the investigation.

Biobank

A study-specific biobank for the duration of the study until five years after all participants are dead will be created.

All blood- and other biological samples collected as part of the study will be stored in this biobank.

Questionnaires and consent forms

Participants will already have completed the Koronastudien questionnaires containing questions about risk factors for Covid-19, supplement use, travel history, cancer, cardiovascular disease, and other previous diseases, skin-type, sunlight exposure, and demographic variables). During the study period, it is expected that 1-2 Koronastudien specific follow-up questionnaires will be distributed, and these will be coordinated to reduce the burden of participation. In addition, the following data will be collected from the sub-study participants using electronic forms:

- Screening questionnaire before inclusion (inclusion and exclusion criteria)
- Consent form. The identity of each participant in Koronastudien is known through the consenting procedure using two-factor authentication with Bank ID. The consent form for Transtudien will be sent as a unique link to existing participants, and consenting will be a simple yes or no checkbox at the end of the form without requiring further identification with Bank ID.
- Baseline questionnaire: Diet including an estimate of vitamin D and n-3 LCPUFA intake and other baseline data collection will be coordinated with a follow-up questionnaire in Koronastudien to reduce participant burden.
- Every month: Compliance, use of supplements, side effects, efficacy of blinding, endpoints
- End of study: FFQ (a validated web-based food frequency questionnaire), risk factors for Covid-19 and other relevant diseases, use of supplements, previous conditions, side effects, efficacy of blinding, endpoints
- Follow-up up to two years: Diet, use of supplements, endpoints.

Participants will also be encouraged to report any symptoms of respiratory tract infections and any possible side-effect during the cod liver oil taking period using an electronic questionnaire available to them at all times during the study period.

Dietary questions on vitamin D and n-3 LCPUFA will be based on the FFQ.

Registries

Data for validation of endpoints, previous diseases, and risk factors will be obtained from the following registries (registry, data to be obtained):

- Causes of death: death, and cause of death
- Hospital records: verification of endpoints
- KUHR: visits to GP and cause of visit
- Norwegian Prescription database:, medications
- MSIS (the Mandatory Norwegian Surveillance System for Communicable Diseases): Covid-19 status,- negative and positive SARS-CoV-2 tests.
- The Norwegian Patient Registry (NPR): Hospital admissions and outpatient visits: fractures, health-related events and endpoints
- The patients' general practitioner or treating physician may be contacted for verification of endpoints, adverse effects, and causes of death

- Luftveisdatabasen (Airway Database), Covid-19 status, other PCR and culture verified infections
- Microbiology laboratories, microbial test results not available through Airway Database (HelseNorge.no)
- Other statutory health registries including the Norwegian Pandemic Registry and heart registry
- Folkeregisteret and The Contact and Reservation Registry, contact information, address
- Quality Registries on Covid in Oslo University Hospital, detailed data about risk factors for Covid-19 and outcome of disease

Assessment of dietary and Supplemental Intake Questionnaire

Simple questions about the intake of vitamin D and n-3 LCPUFAs (based on a validated, selfadministered semi-quantitative food frequency questionnaire (FFQ)) will be distributed to participants at baseline. Classifying participants by baseline intake of various nutrients will allow us to evaluate whether the study agents' effects vary by such intake. Participants will be asked to complete a complete FFQ.

Questions on the use of non-study supplements or drugs containing vitamin D or EPA+DHA will be asked at baseline and end of the study and on follow-up questionnaires. We will ascertain and analyze intake from food and supplements separately, and from both sources combined.

Follow up

At the end of the intervention, three, six months, 12 and 24 months later, a questionnaire will be sent to participants. The form will be similar to the conventional follow-up questionnaires, collecting information about potential risk factors, major diseases use of medications, and medical history. The additional data will be used to address the duration of any effects seen on the primary endpoints and any side effects of the intervention as well as to explore other health effects of cod liver oil as described in the endpoint section.

Data management

The handling data will be closely connected to the handling of data in Koronastudien, and for data handling purposes, the CLOC study will be treated as a sub-study of Koronastudien. An application to process and store data from the two studies together will be sent to the Data Protection Officer at Oslo University Hospital. Koronastudien has been approved by the Data Protection Officer at Oslo University Hospital in accordance with the European GDPR regulations.

The University of Oslo service for sensitive data (TSD) will be used to collect, store, and analyze data. Additionally, HUNT cloud and LEDIDI Prjcts will be used for analyzing data. The data will be analyzed without any directly personally identifying information using a Study ID instead. The patient list connecting the patient identity with the study ID will be kept in a separate folder in TSD, and the backup will be kept at an encrypted USB data storage device. Deidentified data will be backed up at K:/sensitive, a secure location at the Oslo University Hospital's internal web.

9. Statistical considerations

The detailed statistical analysis plan will be approved by the study steering committee before unblinding.

Statistical Hypotheses

See Sample Size Determination and the statistical analysis plan

Sample Size Determination

The fallback method (https://www.fda.gov/media/102657/download) will be used to correct for testing of multiple primary endpoints.

The total alpha (0.05) will be divided among the endpoints, and a fixed sequence for the testing will be maintained. As the testing sequence progresses, a successful test preserves its assigned alpha as "saved" (unused) alpha that is passed along to the next test in the sequence. This passed-along alpha is added to the assigned alpha of the next endpoint, and the summed alpha is used for testing that endpoint. Thus, as sequential tests are successful, the alpha accumulates for the endpoints later in the sequence; these endpoints are then tested with progressively larger alphas.

Endpoints in testing order with power calculation:

1. Serious Covid-19 (Covid-19 with self-reported dyspnea, self-reported hospitalization, or death). Assigned α =0.018.

Based on the observations in Koronastudien of a 40% reduction in serious Covid-19 in the group reporting use of cod liver oil, and an expected incidence of 0.25%, a power of 70%, 67,000 participants will have to be included for this endpoint.

- Covid-19 positive PCR. Assigned α=0.03.
 Based on the observations in Koronastudien of a 20% reduction in Covid-19 incidence in the group reporting use of cod liver oil, and an expected incidence of 1%, a power of 70%, 65,000 participants will have to be included for this endpoint.
- Frequency of negative SARS-CoV-2 tests (MSIS). Assigned α=0.001. Covid tests (SARS-CoV2-2), real time (RT)-PCR, are mostly obtained because of a suspicion of COVID-19. The number of negative covid tests from one week after starting taking cod liver oil/placebo and to the end of the intervention period. This endpoint has been added as an alternative to the Positive PCR or bacterial culture endpoint (secondary endpoint, which is not available at this time).
- 4. Self-reported airway infection (yes/no). Assigned α =0.001. Based on the expected frequency of airway infections in Koronastudien of >30% and as a threshold of clinically interesting reduction of all airway infections of 10%, 23,000 participants will have to be included for this endpoint. The study has a power for this endpoint >95%. 16000 participants in the study will give an 80% power for this endpoint.

Analysis sets

Participants will be assigned to the cod liver oil or placebo group in a 1:1 ratio. The primary endpoints will be calculated using relative risks, Kaplan-Meier plots and Cox regression on the intention to treat (ITT) population with missing data on outcome counting as the negative outcome.

Compliance with cod liver oil taking and power of the study

The power calculation is based on data from Koronastudien and participants reporting taking cod liver oil. We have no data on how often cod liver oil was used by these participants but believe that it is less than once daily on average. Thus, although many participants in the CLOC study will not be fully compliant, we expect that a large majority of participants will have the same level of cod liver oil taking as found in Koronastudien. However, to increase the power, we will attempt to recruit up to 80.000 participants to increase the power of the study.

Interim Analyses

Covid-19-prevalence and power

The power of the study is dramatically influenced by the incidence of Covid-19, and this will be considered when the statistical analysis plan is finalized before unblinding to maximize the scientific output of the study. Thus, the statistical analyses including p-values and testing-order above can be changed if the Covid-19 situation dictates such changes. Any change will be done before unblinding. The time of unblinding can be changed based on the prevalence of Covid-19 to increase the scientific output from the study. No interim analyses will be conducted.

10. Ethics

Risks in the cod liver oil group

Cod liver oil has been used as a supplement for more than 100 years and thus has an excellent safety record. It is explicitly mentioned under the seafood category in official Norwegian dietary advice (https://helsenorge.no/kosthold-og-ernaring/kostrad/spis-fisk-oftere) The main constituents, vitamin D and omega 3 have been used in tens of thousands of participants in well-designed studies with very few side effects [4, 8]. The risk of overdosing is very low because of the relatively large volume of oil that has to be ingested for overdosing.

In a Norwegian study with a similar design as the proposed study also with cod liver oil, it was found that 5 ml of cod liver oil increased the vitamin D level with 17 nmol/liter. This is a moderate increase that will have a very low probability of toxicity, yet still be large enough to treat vitamin D deficiency[9]. To further ensure participants' safety, we will exclude from the trial persons with a history of kidney stones, hypercalcemia, renal failure, cirrhosis, or sarcoidosis or other granulomatous diseases and persons belonging to groups advised to use a vitamin D supplement.

We expect no adverse events related to taking cod liver oil and although possible adverse health effects will be monitored as part of the study, adverse events during the cod liver oil taking period will be expected to be followed up as part of normal care by the relevant health professionals and will not be followed up or reported as part of the study.

Risks in the placebo group

Volunteers older then 75 years old are advised use a vitamin D supplement, according to official dietary advice, and will be excluded from the study in the screening phase and receive an automated message about the official advice if they do not report taking and supplement.

The study aims to identify the health effects of cod liver oil as a supplement to the normal diet of participants not normally using such supplements. Most people have a relatively stable diet over many years, and the study will attempt not to interfere with the diet of participants. We consider that continuing to have the same diet as before during a study period that lasts less than one year poses a negligible risk to participants.

However, the Norwegian dietary recommendations for vitamin D are complicated and depend on how much fish you eat, your age, the season, and your sun exposure. Based on the collected data, participants at high risk for vitamin D or low levels of n2-LCPUFFA will be notified at the end of the study and recommended to discuss their diet with their general practitioner and or get their vitamin D levels and 3n-LCPUFA levels measured.

No measurements of vitamin D or 3n-LCPUFA will be made before unblinding, and this will not be known to the study during the cod liver oil/placebo taking period.

Expected side-effects

Several side-effects have been described for intake of fish oil and low-dose vitamin D, but in practice, very few serious side effects are expected to be found.

For fish oil the following side effects have been described: gastrointestinal (GI) symptoms (stomach upset or pain, nausea, constipation, diarrhea), bleeding (any GI bleed, GI bleeding requiring transfusion, hematuria, easy bruising, epistaxis), skin rash, colds or upper respiratory tract infection, flu-like symptoms, bad taste in the mouth

For vitamin D, the following side effects have been described: GI symptoms as listed above, and hypercalcemia or kidney stones.

Each follow-up questionnaire will contain questions about side-effects.

Importance of study results and generalizability

There is a significant inherent risk in the study that the Covid-19 prevalence becomes much lower than the threshold for detection of any effect or that a Covid-19 cure or vaccine becomes available, making the study results less relevant. However, the primary endpoints of respiratory tract infections will still be of great importance; likewise, the in-depth safety characterization of cod liver oil will be of importance.

Benefits

The main benefit of the study is to identify a new and safe way to prevent Covid-19 or its complications. Furthermore, the study is powered to detect whether cod liver oil can prevent respiratory infections. In addition, the study is well suited to compare positive or negative health effects of cod liver oil In particular, the systematic collection of negative health effects that will be conducted is important to ensure the two year safety of this widely used supplement.

Surveying of risks

A survey of risks of the study will be conducted by the PI and in collaboration with the Department of Research Support, OUH and identified risks will be addressed before the beginning of the cod liver oil taking period.

Ethics summary

In conclusion, the study has a low risk of negative health- or other effects on participants and a high probability of identifying whether cod liver oil can prevent Covid-19 and other respiratory infections. Furthermore, the encouraging preliminary data suggests that the morbidity caused by Covid-19 will be significantly reduced in the cod liver oil group adding to the benefit of the study. Further adding to the benefit is the prospect of collecting high-quality data on the more general health effects of cod liver oil use.

In total, we consider that the benefits of the study far outweigh the risks and disadvantages.

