 - Any self-reported airway infections during the period from one week after start of cod liver oil/placebo consumption (*deriv_Date_CLO_start_corr*) to June 2, 2021.
 - Self-reported airway infections criteria
 - Variable: *deriv_respinf_date_yn*

- Answered question *has had respiratory infection since last cloc report* in any CLOC questionnaire (R1-R6)
 - *deriv_respinf_report_yn_ever*
- Date of self-reported airway infections in the period from one week after start of cod liver oil/placebo consumption (*deriv_Date_CLO_start_corr*) to June 2, 2021.
 - *deriv_respinf_date_sums*
-
- Supplementary variable
 - *deriv_respinf_count_report_sum*
 - Number of respiratory infections reported
 - *Rx_Date_respiratoryinfectionx_sym_start_report*
 - Date of each infection reported in each report form

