*Influenza virus (A and B), parainfluenzavirus (1,2,3), metapneumovirus, rhinovirus, coronavirus (non-SARS), Respiratory Syncytial virus, Haemophilus Influenzae, Moraxella Catharralis, Streptococcus Pneumonia, Beta-hemolytic streptococci, Mycoplasma pneumonia, Chlamydophila pneumonia, Enterovirus, Bordetella pertussis. The list can be expanded based on the analyses performed in Norwegian Microbiology laboratories.

Exploratory during follow up of up to two years

- Cardiovascular disease incidence and mortality during the study period or follow up
- Cancer incidence and mortality during the study period or follow up
- All-cause mortality during the study period or follow up
- Fracture of the hip or forearm during the study period or follow up
- Incident dementia during the study period of follow up

Endpoints at six months:

All primary endpoints tested in the final statistical analysis plan will be tested six months after unblinding (the end of the cod liver oil or placebo taking period).

Safety

The safety of the intervention will be followed for two years after the end of the cod liver oil taking period. This will be done by observing all-cause mortality and hospital admissions for major disease groups in the cod liver oil versus the placebo group in Norwegian registries.

4. Study Design

Overall Design

The CLOC study will include 80.000 participants that will be randomized in a 1:1 ratio to consume 5 ml cod liver oil or placebo (corn oil) with lemon taste per day for 6-12 months.

The study will be organized as a ancillary study of "Koronastudien", a cohort study investigating Covid-19. Participants will be a subgroup of participants in Koronastudien, and relevant data from these participants will be shared among the studies.

Koronastudien has collected extensive electronic questionnaire data using the University of Oslo webbased solution "Nettskjema". Koronastudien aims to identify risk factors associated with the community- and workplace acquisition of Covid-19 virus and also aims to identify risk factors for the progression of the disease and to understand the virus and disease themselves.

Scientific Rationale for Study Design

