Under the current pandemic with thousands of deaths daily worldwide, there is an urgent need to rapidly identify possibly safe and efficient preventive measures against Covid-19 and the complications of the disease. The study is designed to obtain such evidence in a timely manner without exposing the participants to unnecessary risk.

Justification for Dose

The most commonly used daily dose of cod liver oil is 5 ml and this dose will also be used in the study. This dose has been shown to increase the vitamin D levels of volunteers significantly, and contains the daily requirement of vitamin D in for most adults in Norway.

End of Study Definition

The End of study is defined as the last day of cod liver oil taking in the spring of 2021. (Participants will still be followed after this date.)

5. Study population

Inclusion criteria

Any person >18 years with a Norwegian Personal Identity Number

Exclusion criteria

An electronic questionnaire will be used to collect self-reported data about exclusion criteria.

- History of renal failure or dialysis, hypercalcaemia, severe liver disease (chirrosis), sarcoidosis or other granulomataous disease (Wegener)
- Allergy to fish or corn oil.
- Pregnancy or planned pregnancy before summer 2021
- Vegan diet
- Age >75 years old at inclusion based on the Norwegian Personal Identity Number
- Difficulty of swallowing cod liver oil or other oils
- Previous Covid-19 disease
- For Caucasians only: Use of any supplement containing more than trace amounts of vitamin D or omega-3 fatty acids at inclusion (Vitamin D levels in non-Caucasians living in Norway are frequently low even among those self-reporting using dietary supplements).

 This criteria will be relaxed if too few participants volunteers to the study and only Caucasians that use cod liver oil or an equivalent dietary supplement (with vitamin D) more than 5-7 times per week will be excluded. Furthermore, Caucasians that use supplements with omega-3 fatty acids will not be excluded.

Lifestyle Considerations

No restrictions are required

Recruitment

A large number of participants must be recruited in a short period of time. The following recruitment strategies will be employed:

- 1. The CLOC invitation letter and screening questionnaire will be sent to Koronastudien participants.

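### The six-month re-test covers all primary endpoints, but after oil-taking the self-reported ones come from sparser forms and possibly from participants who know their arm, so they cannot carry a claim about duration of effect

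*Combined protocol and SAP*

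**What the plan says.** Protocol section 3, under Endpoints at six months, commits that "All primary endpoints tested in the final statistical analysis plan will be tested six months after unblinding", and in parentheses equates unblinding with the end of the oil-taking period. Protocol section 8 (Follow up) gives the purpose: "The additional data will be used to address the duration of any effects seen on the primary endpoints".

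The two periods are measured differently:

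- **During oil-taking.** Protocol section 8 (Questionnaires and consent forms) lists "Every month: Compliance, use of supplements, side effects, efficacy of blinding, endpoints". Participants may also report symptoms "using an electronic questionnaire available to them at all times during the study period"; the same sentence ties this to the oil-taking period. Section 4 adds that "The End of study is defined as the last day of cod liver oil taking in the spring of 2021". The trial is described as triple-blinded.
- **After oil-taking.** "At the end of the intervention, three, six months, 12 and 24 months later, a questionnaire will be sent to participants". The content is summarised as "Follow-up up to two years: Diet, use of supplements, endpoints". No question on the efficacy of blinding is listed here, although it is listed for the monthly and end-of-study forms.

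The SAP defines no six-month analysis. In Appendix 1, endpoint 4 uses only questionnaires R1 to R6, asks about infection since the last report, needs a valid date for a Yes, and closes on June 2, 2021. Section 6.3 counts no positive answer as No. Endpoints 2 and 3 come from MSIS.

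**The concern.** A statement about how long an effect lasts compares two periods, so it needs the same measurement in both. Here the form schedule, the recall window and the any-time form all change when the oil stops, and masking may change as well. Endpoint 4 depends wholly on the forms. Endpoint 1 depends on them for dyspnoea and hospitalisation. Neither document addresses the change.

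Two errors are possible. A lower reported rate after oil-taking could be read as a real change in risk or in absolute benefit. A between-arm difference created by participants who know what they took could be read as a lasting benefit.

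**Working it through.** **1. The plan's own figure.** No figure is given for the six-month test. For endpoint 4 during oil-taking the inputs are 30% versus 27%, alpha 0.001 and 1:1 allocation (SAP 3.3). Let d be the difference between the two risks, p̄ their mean and n the number per arm. Power is Φ[(d − z·SE₀)/SE₁], with SE₀ = √(2p̄(1−p̄)/n), SE₁ = √((p₀(1−p₀)+p₁(1−p₁))/n) and z = 3.29 (two-sided).

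- n = 8,000: d = 0.03, SE₀ ≈ SE₁ ≈ 0.00714, power 0.82 (plan: 80% at 16,000).
- n = 11,500: SE₀ ≈ SE₁ ≈ 0.00595, power 0.96 (plan: above 95% at 23,000).

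The plan's figures reproduce.

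**2. Longer recall, equal in both arms.** The gap between forms grows from about 30 to about 91 days up to month 6. Assume that recall of a dated infection decays with half-life h (60 to 180 days; not in the documents). The mean share recalled over a gap L is (1 − e^(−λL))/(λL), with λ = ln 2/h. Use this as sensitivity (Se) and hold specificity (Sp) at 0.98 (assumption). Reported risk is p·Se + (1−p)·(1−Sp), with p = 0.30 and 0.27, so the risk difference is −0.03 × (Se + Sp − 1).

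| h (days) | Se, 30 → 91 days | Relative fall in Se | Risk ratio | Risk difference (points) | Power at N = 16,000, alpha 0.001 |
|---|---|---|---|---|---|
| 60 | 0.845 → 0.619 | 27% | 0.9075 → 0.9100 | −2.48 → −1.80 | 0.618 → 0.345 |
| 90 | 0.893 → 0.719 | 19% | 0.9071 → 0.9087 | −2.62 → −2.10 | 0.672 → 0.466 |
| 180 | 0.944 → 0.844 | 11% | 0.9067 → 0.9075 | −2.77 → −2.47 | 0.726 → 0.616 |

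The risk ratio moves by 0.003 at most. With no false reports it stays exactly 0.90. The risk difference and power do fall. The power loss matters at the plan's 16,000 benchmark; at 80,000 with Se 0.60 and Sp 0.98 power is still 0.999. The 30% is an on-oil figure, and the documents give no post-oil rate.

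**3. Answers given with knowledge of the arm, no true effect.** Assume 18% reporting (0.30 × 0.60), 33,500 per arm (half of the plan's 67,000 for endpoint 1), and relatively fewer reports by a fraction r in the oil arm. No alpha is assigned to the six-month test, so both 0.05 and 0.001 are shown.

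| r | d | SE₀ | d/SE₀ | P(reject), 0.05 | P(reject), 0.001 |
|---|---|---|---|---|---|
| 2% | 0.0036 | 0.002957 | 1.22 | 23% | 2% |
| 5% | 0.0090 | 0.002939 | 3.06 | 86% | 41% |
| 10% | 0.0180 | 0.002909 | 6.19 | >99% | 99.8% |

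The result also depends on the rate. At 80,000 participants, r = 5% and alpha 0.001, it is 18%, 61% and 92% for reported rates of 10%, 20% and 30%.

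**4. When unblinding occurs.** Protocol section 3 equates it with the end of oil-taking. SAP 3.3 and protocol section 9 require the analysis plan to be settled first. SAP 1.4 shows approval on 24 November 2021 and an amendment on 10 December 2021, both marked pre-analysis. The latter is 191 days after June 2, 2021. On those dates the 3- and 6-month forms would precede unblinding, and a test six months after unblinding would fall near the 12-month form or later. No section says when participants are told their arm.

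**The case against.** The strongest reply has four parts.

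- **The comparison is still randomised within the post-oil period, and longer recall affects both arms alike.** This stands for the risk ratio. A reader might infer that sparser forms by themselves make a constant effect look as if it wanes. The documents do not support that. Moving the observed ratio from 0.907 to 0.940 (3.3 points) requires specificity to fall to 0.90 as well as sensitivity to 0.60. Nothing in the plan suggests such a rise in false reports, and the valid-date rule works against it.
- **Unblinding at the end of oil-taking is not settled.** This also stands. One parenthesis supports it and other text points later. But a test placed six months after unblinding draws on a period following unblinding, whichever date applies. If participants are told their arm, those answers are unmasked.
- **Endpoint 1 is better protected.** It needs an MSIS positive, dyspnoea counts if ever reported on any listed form after the test, participants with a positive result and no symptom form are prompted, and Covid-related hospital diagnoses and deaths are checked against records with blinded review. This stands in part: a fall in reported endpoint 1 is not shown. Dyspnoea remains self-reported, and the SAP derives hospitalisation from the forms.
- **Registry endpoints are not immune.** The plan itself says that tests are mostly taken on suspicion of Covid-19, so test-seeking could change once allocation is known. This stands and belongs in the fix as a caveat.

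The gap could be left to a later SAP, but SAP 3.6 promises one only for secondary variables.

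**Conclusion.** The concern holds in a limited form. For endpoint 4 and the self-reported parts of endpoint 1, reported rates during and after oil-taking are not comparable, and the plan uses follow-up data to address duration of effect without allowing for this. More under-reporting is expected. It would shrink the absolute difference (for example from −2.48 to −1.80 points at a 60-day recall half-life) and reduce power, with almost no effect on the risk ratio.

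The main risk of bias is reporting that differs by arm once participants know their allocation. Its size is unknown. With this many participants a 5% relative shift would often be significant, while a 2% shift usually would not. The half-lives, specificity, reporting rate and shifts are all assumptions. The risk also depends on participants being told their arm before they answer, which the documents leave open. The analysis of the oil-taking period is not affected.

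**What to change.** In protocol section 3 (Endpoints at six months), and in the SAP:

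1. Base the six-month test and any statement on duration of effect on registry-ascertained endpoints with the same definition in both periods. These are endpoints 2 and 3 from MSIS, with a note that test-seeking may change once allocation is known. For serious Covid-19, use hospitalisation and death from the registries already planned in protocol section 8. For this comparison the on-oil hospitalisations must come from the registry too, because the SAP takes them from self-report.
2. Report endpoint 4 and self-reported dyspnoea and hospitalisation after oil-taking as a separate, supportive comparison between arms. Split it at the date participants learn their allocation, and do not compare these rates with the on-oil rates.
3. Reconcile the unblinding date across protocol section 3, protocol section 9, SAP 1.4 and SAP 3.3, and state when participants are told their arm.
4. State the window, alpha and status of the six-month test.

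The cost is wording in both documents, plus the date on which participants learn their allocation and registry data for both periods, which are already planned. The downside is that there is no confirmatory six-month claim on the self-reported endpoints.
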